1.2.2 Clinical Studies

One Phase I study has been conducted to date (Study ALN-PCSSC-001). This was a randomized, single-blind, placebo-controlled, single-dose escalation and multiple-dose study of inclisiran administered SC to subjects with elevated LDL-C. The study was conducted in two phases: a single ascending dose (SAD) phase and a multiple dose (MD) phase. During the SAD phase, 24 subjects were assigned to either receive placebo or one of five doses of inclisiran ranging from 25 mg to 800 mg. Those who received doses of at least 100 mg saw their LDL-C drop at least 40%; at the 500 mg dose, LDL-C levels dropped as much as 78%. At 140 days after the treatment was given, subjects still had an average LDL-C reduction of about 40%.

In the MD phase, 45 subjects received multiple doses of either inclisiran (125mg weekly x4, 250 mg biweekly x2, 300 mg and 500 mg twice given 1 month apart) or placebo. These subjects had maximal LDL-C reductions of 80% and average LDL-C reductions of 50% to 60%. To date, the drug appears to be generally safe and well tolerated. One subject on statin comedication had elevated liver enzymes with alanine aminotransferase (ALT) >4x the upper limit of normal (ULN), which resolved on stopping the statin.

One Phase II dose finding study CKJX839A12201 (MDCO-PCS-15-01; ORION-1) was conducted and is complete. This study was a placebo-controlled, double-blind, randomized trial to compare the effect of inclisiran administered SC as either a single dose (200 mg, 300 mg, or 500 mg) on Day 1 or as two doses (100 mg, 200 mg, or 300 mg) on Day 1 and Day 90 in subjects with high cardiovascular risk and elevated LDL-C. A total of 501 subjects were randomized (placebo=127 and inclisiran=374) and 497 received at least one dose of study drug (placebo=127 and inclisiran=370). After administration of dosing, all subjects were followed until Day 210. Subjects whose LDL-C values had not returned to within 20% of the change from their baseline value were followed up to Day 360. Regular reviews of safety were performed by an independent Data Monitoring Committee and no safety concerns were reported and no changes to the protocol were requested during conduct of the study.

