6.2 General Conduct of the Study

On completion of study MDCO-PCS-15-01 (ORION-1), eligible subjects will be consented for this study. Written informed consent will be obtained for this study by the principal investigator or sub-investigator from all subjects before the performance of any protocol-specific procedure. In countries where applicable, on signing consent and being entered into this study, the investigator will be informed by the IXRS regarding the treatment allocation, and therefore, whether placebo or inclisiran was administered in study MDCO-PCS-15-01 and the subject will be informed accordingly.

Until study drug is available subjects will attend a basic visit for safety and concomitant medications at 30 day intervals. Once study drug is available, eligible subjects will receive a single injection of study drug on Day 1 (ORION-3).

Note: Data on medical history and concomitant medications will be reported from Baseline of ORION-1. Details will be described in the Statistical Analysis Plan (SAP).

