7.1.6 Clinical Laboratory Assessments

Specimens will be obtained at the time points in the Schedule of Assessments ([Table 6-1](#) and [Table 6-2](#)). Additional aliquots of plasma or serum will be collected at each time point and stored for any clinically indicated efficacy or safety analyses to be conducted at the end of the study.

Subjects will be in a fasted state for all clinical laboratory assessments. Details regarding the processing, shipping, and analysis of samples will be provided in the Laboratory Manual. Note: Efficacy laboratory assessments (eg, LDL-C and PCSK9) are described in [Section 7.2](#).

Laboratory assessments will include:

Hematology – Day 1, Day 360, Day 720, Day 1080 and EOS: hemoglobin, hematocrit, erythrocytes, reticulocytes, platelet counts, mean cell hemoglobin (MCH), mean corpuscular

volume (MCV), mean corpuscular hemoglobin concentration (MCHC), white blood cell count, differential blood count.

Coagulation - Day 1, Day 360, Day 720, Day 1080 and EOS: prothrombin time (PT), international normalized ratio (INR), activated partial thromboplastin (aPTT). Coagulation samples will also be collected at all other visit, however, these samples will be stored for any clinically indicated safety analyses to be conducted at the end of the study.

Chemistry

Blood draws for chemistry will be performed per the Schedule of Assessments (Table 6-1 and Table 6-2). Analysis will vary based on visit day as follows:

- **Full serum chemistry - Day 1, Day 360, Day 720, Day 1080 and EOS**

AST, ALT, alkaline phosphatase (ALP), gamma glutamyl transferase (GGT), total bilirubin (TBIL), uric acid, creatine phosphokinase, albumin, total protein, urea (BUN), creatinine, sodium, potassium, chloride, inorganic phosphate, , direct and indirect bilirubin, , estimated glomerular filtration rate (eGFR), calcium, and bicarbonate.

- Fasting serum glucose and glycated hemoglobin A1C (HbA1C): Days 1, 1080 and EOS only
- High sensitivity C-reactive protein (hsCRP) (fasting): Days 1, 360, 720 and EOS only.

- **Limited serum chemistry all subjects – Days 30, 90, 180, 270, 390, 450, (510 Group 2 only), 540, (570 Group 1 only), 630, 810, (870 Group 1 only), (900 Group 2 only), 990, 1170, 1260, and 1350**

ONLY: AST, ALT, ALP, GGT, TBIL, CPK, creatinine, eGFR, and tryptase (as required).

- Fasting serum glucose and HbA1C: Days 270, 540, 810 and 1350 only

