8.2.4.2 Other Safety Related Information

Injection site reactions (ISR) including individual signs or symptoms at the injection site following investigational product administration should be recorded on specifically designed eCRF pages. Photographs of ISR, if they were obtained during the study visits, should be forwarded to study inbox.

Other safety related information that requires collection, evaluation and reporting safety information in this study are:

- Abnormal neurological examination, eg, peripheral sensory and motor evaluation, an assessment of gait, pain, position, strength and reflexes ([APPENDIX A](#)).
- Potential anaphylactic reactions assessed by Sampson criteria ([APPENDIX B](#)). If Sampson criteria are positive, confirm by elevation of tryptase in blood plasma measured within 30 minutes of symptoms.

Hyperglycemia-related AEs and medications initiated to control hyperglycemia will be collected at each follow-up visit. New onset of diabetes in subjects with no medical history of diabetes will be reported when:

- HbA1C becomes $\geq 6.5\%$ and/or
- Two consecutive values of fasting plasma glucose that are ≥ 126 mg/dL

In the case that a new concomitant medication is added for control of plasma glucose, further information regarding the subject will be collected to assess for a diagnosis of new onset diabetes.

Report 'Worsening of the glycemic control' or 'diabetic complications' in subjects with a medical history of disease (HbA1C $\geq 6.5\%$ at baseline) when:

- HbA1C increases from Baseline (Day 1 of ORION-3) $>0.5\%$ and/or
- New concomitant medication or increase in dose of current antidiabetic therapy is initiated to improve the control of plasma glucose level.

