**Table 2-1 Summary of baselines**

Analysis category	Analysis	Baseline used	Explanation
Baseline Characteristics	Age*, weight, body mass index (BMI), country	Study entry of ORION-3	To provide a more accurate value of parameters that may change, baseline of ORION-3 is used.

	Estimated glomerular filtration rate (eGFR)	Last non-missing record prior to first study drug administration of ORION-3	To provide a more accurate value of parameters that may change, baseline of ORION-3 is used.
	Sex, race, ethnicity, height	Screening period of ORION-1	These values will not change or will not change significantly so baseline of ORION-1 is used.
	Medical history	Day 1 of ORION-1	Medical history is reported prior to the first treatment in ORION-1, after which any new medical conditions will be captured as AEs.
Prior and concomitant therapies	Concomitant Medications	Day 1 of ORION-3	Medications taken on or after Day 1 of ORION-3 will be considered as concomitant for ORION-3.**
Efficacy	Efficacy parameters in Group 1 (inclisiran only arm)	Baseline of ORION-1***	Due to residual efficacy from ORION-1, the true change from baseline should use baseline of ORION-1, i.e. prior to receiving any dose of inclisiran.
	Efficacy parameters in Group 2 (switching arm)	Baseline of ORION-3****	Placebo was given in ORION-1 and since treatment adjustments may have occurred during ORION-1 in lipid modifying therapies (LMT), baseline of ORION-3 will be used.
Safety	Adverse events	Day 1 of ORION-3	Previous AEs are collected in ORION-1, the gap period and the observation period so TEAEs in ORION-3 are collected from Day 1 (first dose) of ORION-3.
	Electrocardiograms (ECG)	Day 1 of ORION-3	To identify untoward change in ECG within ORION-3
	Safety laboratory parameters, vital signs	Baseline of ORION-3****	To identify untoward change in safety laboratory parameters and vital signs within ORION-3

\* Since age will not be re-collected in ORION-3, the age at ORION-3 baseline is inferred using the ORION-1 baseline:

- If the difference between consent date in ORION-3 and ORION-1 is greater than 365 days for a subject then 1 year will be added to the age at ORION-1 baseline;
- Otherwise, ORION-1 baseline age will be used.

\*\* Although all medications received 30 days prior to consent in ORION-1 through the EOS in ORION-3 will be reported, only medications taken on or after Day 1 of ORION-3 will be considered concomitant for ORION-3.

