## **2.7 Safety analyses**

All safety evaluations will be performed for the following groups unless otherwise specified:

- Subjects on evolocumab from the switching arm (Group 2) for the period between Day 1 (Day 1 of ORION-3) and Day 360.
- Subjects from the inclisiran only arm (Group 1), for the period from Day 1 (Day 1 of ORION-3) until EOS.

█ [REDACTED]

█ [REDACTED]

█ [REDACTED]

All the safety analyses will be performed on the safety population unless otherwise specified. Safety analyses are based on observed values. Any missing safety data including laboratory data will not be imputed.

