#### 2.7.4.4 Incidence of post-baseline new-onset of diabetes

The number of subjects who shift from no diabetes at baseline (defined as no medical history of diabetes in the targeted medical history CRF, HbA1c <6.5% at baseline, and fasting glucose <126 mg/dL at baseline (note that baseline is defined as the average of study entry and Day 1

fasting glucose values. If one fasting glucose value is missing (study entry or Day 1), the assessment will be based on the available data) to diabetes will be summarized. A 4-component definition of diabetes will be utilized. The 4 components are provided below.

1. Diabetic TEAEs identified by the search criteria in [Appendix 5.2](#), or
2. Post-baseline fasting glucose  $\geq 126$  mg/dL on two consecutive occasions, or
3. Initiation of anti-diabetic medication (ATC level 2 code: A10) at any time post-baseline, or
4. At least one post-baseline HbA1c  $\geq 6.5\%$ .

The number of subjects who have any of the 4 components (post-baseline new-onset of diabetes) will be summarized along with each component. This analysis will be performed for those subjects who have fasting glucose at baseline  $< 100$  mg/dL and then for those with fasting glucose at baseline  $\geq 100$  and  $< 126$  mg/dL.

The time to new-onset diabetes will also be summarized. Only subjects without diabetes at baseline will be included in the analysis. The time (weeks) to new-onset diabetes will be calculated from the date of the first administration of study drug.

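### The new-onset diabetes summary (SAP 2.7.4.4) keeps in its at-risk set subjects whose diabetes began between the ORION-1 and ORION-3 baselines and is below the laboratory cut-offs at ORION-3 baseline: minor, and cheap to correct

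*SAP*

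**What the plan says.** SAP 2.7.4.4 sets three conditions for having no diabetes at baseline. The first is historical, "defined as no medical history of diabetes in the targeted medical history CRF". The other two are laboratory tests: HbA1c below 6.5% and fasting glucose below 126 mg/dL. Glucose is the average of ORION-3 study entry and Day 1. SAP 2.7.4.2 takes baseline HbA1c from ORION-3 Day 1, or from study entry if that is missing.

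The history has a different date. SAP Table 2-1 places it at ORION-1 Day 1 and gives this reason: "Medical history is reported prior to the first treatment in ORION-1, after which any new medical conditions will be captured as AEs". Protocol 6.2 agrees: "Data on medical history and concomitant medications will be reported from Baseline of ORION-1". SAP 2.3.2 treats the targeted history as part of medical history.

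A subject then counts as new onset through any one of four components: a diabetic TEAE (1), two consecutive fasting glucose values of at least 126 mg/dL (2), initiation of an A10 drug (3), or one HbA1c of at least 6.5% (4). Time to onset runs from the first study drug dose, which SAP 2.1.1 defines as the first dose in ORION-3.

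Protocol 8.2.4.2 also relies on history: "New onset of diabetes in subjects with no medical history of diabetes will be reported when" laboratory criteria are met.

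**The concern.** The SAP says that a condition arising after the first ORION-1 dose is recorded as an adverse event, not as history. Yet 2.7.4.4 does not look at adverse events before ORION-3 Day 1, or at anti-diabetic drugs in use on that day, when it decides who is at risk. Treatment tends to bring both laboratory values below their cut-offs, so treated cases are the ones these two tests are most likely to miss.

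At stake are the meaning of the new-onset count and of the time to onset, both of which could include disease that began before ORION-3. In Group 1 this is mainly an error of dating, because inclisiran exposure began in ORION-1. In Group 2 the ORION-1 treatment was placebo, so an earlier onset could be placed in the evolocumab period, which SAP 2.7 summarises separately: "Subjects on evolocumab from the switching arm (Group 2) for the period between Day 1 (Day 1 of ORION-3) and Day 360".

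**Working it through.** The documents give no figure for this point, so there is none to reproduce. The check is mainly textual.

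**1. Following one subject through the rule.** Suppose diabetes is diagnosed between ORION-1 Day 1 and ORION-3 Day 1, and HbA1c and glucose are below the cut-offs at ORION-3 baseline.
- Targeted history: negative, because it predates the diagnosis.
- HbA1c and fasting glucose: both pass.
- Result: no diabetes at baseline, so at risk.

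An interim case that is above either cut-off is removed by the laboratory tests.

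**2. How that subject can be counted later.**
- Component 4: one HbA1c of at least 6.5%.
- Component 2: two consecutive fasting glucose values of at least 126 mg/dL.
- Component 3: a first or an added A10 drug. The text does not require that no A10 drug was in use at Day 1.
- Component 1: less often. SAP 2.7.1 counts an event already present only if its severity increased. But TEAEs are classed by preferred term, and the Appendix 5.2 search includes diabetic complications and glucose-test terms, so a new term can qualify.

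A subject who triggers none of these adds only to the denominator. The direction of the error in the proportion is therefore not fixed.

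**3. Length of the interval.** Enrolment requires ORION-1 follow-up to at least Day 210 (Protocol 10.1). At least 7 days separate study entry or the last observation visit from Day 1 (Table 6-1, footnote q).
- Minimum: 210 + 7 = 217 days; 217/365.25 = 0.59 year.
- If ORION-1 Day 360 was reached: 360 + 7 = 367 days; 367/365.25 = 1.00 year.
- Any gap or further observation time is added to these.

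**4. Group 2, evolocumab period.** Protocol 7.1.6 lists "Fasting serum glucose and HbA1C: Days 270, 540, 810 and 1350 only" under limited chemistry and "Fasting serum glucose and glycated hemoglobin A1C (HbA1C): Days 1, 1080 and EOS only" under full chemistry. The only scheduled post-baseline HbA1c up to Day 360 is therefore Day 270, at (270 − 1)/7 = 38.4 weeks. Components 1 and 3 can act at any time in the period. For component 2 the documents differ:
- On 7.1.6, the first two scheduled glucose tests are Days 270 and 540, so the earliest completion is (540 − 1)/7 = 77.0 weeks, after the switch.
- Footnote d of Tables 6-1 and 6-2 says that chemistry includes glucose, and full chemistry is scheduled at Day 360. On that reading the earliest completion is Day 360, at (360 − 1)/7 = 51.3 weeks.

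**5. Scale, component 4 only.** Let k be the number of such subjects in Group 2 and p the chance that one HbA1c is at least 6.5%. Both are assumptions. The ceiling for k is the 127 subjects who received placebo in ORION-1 (Protocol 1.2.2). The expected number wrongly counted at Day 270 is k × p:

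| k | p = 0 | p = 5% | p = 10% | p = 20% |
|---|---|---|---|---|
| 1 | 0 | 0.05 | 0.10 | 0.20 |
| 2 | 0 | 0.10 | 0.20 | 0.40 |
| 5 | 0 | 0.25 | 0.50 | 1.00 |

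Over the whole study there are six scheduled HbA1c tests (Days 270, 540, 810, 1080, 1350 and EOS). The chance per subject lies between p (results fully correlated) and 1 − (1 − p)^6 (independent). That gives 5–26%, 10–47% and 20–74% for p = 5%, 10% and 20%. The upper ends are outer bounds, because repeat values in one person are correlated.

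**6. Illustrative number of such subjects, both groups.** Assume that 60–80% of the 382 enrolled had no diabetes at ORION-1 Day 1, incidence is 1–3 per 100 person-years, the interval is 210–540 days (540 is an assumed upper value), and 30–70% of interim cases are below both cut-offs.
- Low: 382 × 0.6 × 0.01 × (210/365.25) × 0.3 = 0.4.
- High: 382 × 0.8 × 0.03 × (540/365.25) × 0.7 = 9.5.

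Suppose every one were later counted, and genuine onset ran at the same rate over 1440 days. The excess relative to genuine cases would then be 210 × 0.3/1440 = 4% to 540 × 0.7/1440 = 26%. This is a ceiling under the assumptions, not an estimate.

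**The case against.** The case for leaving the text alone is reasonable. The SAP follows the protocol's history rule and tightens it with two ORION-3 laboratory exclusions. The output is descriptive, each component is tabulated, and the listings show all adverse events, including those before dosing. No hypothesis or decision depends on the count. The CRF was not available for review, and some schedule rows and safety comparison groups are blacked out. All of this stands. It limits the weight of the point but does not close the gap in the definition.

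A second objection concerns the remedy. SAP 5.1.3 classes a drug with both dates missing as baseline concomitant. If that flag defined the exclusion, a subject who really started an A10 drug during ORION-3 could be dropped, along with any laboratory evidence. This is correct, and the fix has to avoid that default.

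Two stronger readings should also be resisted. A reader might infer that misattribution in the evolocumab period depends on the Day 270 HbA1c alone. It does not, since components 1 and 3 can act at any time in that period. A reader might also infer that component 2 cannot complete before Day 540. The conflict between Protocol 7.1.6 and footnote d leaves that open.

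**Conclusion.** The gap is real on the SAP's own text: history is dated at ORION-1 Day 1, the laboratory tests at ORION-3 baseline, and nothing in the at-risk definition covers the interval between them. It is a minor point. The number of affected subjects is not in the documents and may be zero. The k × p figures rest on assumed values and cover component 4 only, so they are not the full chance of being wrongly counted.

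It would be tempting to conclude that the new-onset count is materially inflated, or that evolocumab is put at a disadvantage. The documents do not support either: they give no diabetes incidence and no number of interim cases, and the 26% ceiling requires every such subject to be counted later. The primary endpoint is not affected.

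**What to change.** In SAP 2.7.4.4, also exclude from the at-risk set any subject with:

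- (i) an adverse event denoting diabetes mellitus, using the Diabetes Mellitus high level term in Appendix 5.2, with a known onset before ORION-3 Day 1; or
- (ii) an A10 drug with a documented start before ORION-3 Day 1 and ongoing on that day, with the indication checked.

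State that the missing-date default in SAP 5.1.3 does not apply here. Report the number excluded under each criterion. Optionally, add the same two criteria to the baseline-diabetes strata in 2.7.4.1 and leave the rest of that definition unchanged.

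The cost is a few lines of SAP text and programming, plus a short review of indications. SAP Table 2-1 confirms that adverse events from ORION-1, the gap period and the observation period are collected, as are medications from 30 days before ORION-1 consent. The downside is a slightly smaller at-risk set and a small chance of excluding someone who takes an A10 drug for another reason. If no subject meets either criterion, the tables do not change.

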## **2.7.5 Other safety data**

### **2.7.5.1 Electrocardiograms (ECG)**

The percentage of subjects with any changes from baseline ECG will be summarized over time.

### **2.7.5.2 Vital signs**

Observed value, change, and percent change from ORION-3 baseline in vital signs will be summarized descriptively at each scheduled time point by treatment group.

The change from baseline to EOS will also be summarized by the following categories:

- Systolic blood pressure (mmHg):
  - $\leq -20$
  - $> -20$  to  $\leq -10$
  - $> -10$  to  $\leq -5$
  - $> -5$  to  $< 5$
  - $\geq 5$  to  $< 10$
  - $\geq 10$  to  $< 20$
  - $\geq 20$
- Diastolic blood pressure (mmHg):
  - $\leq -10$
  - $> -10$  to  $\leq -5$

- $> -5$  to  $\leq -3$
- $> -3$  to  $< 3$
- $\geq 3$  to  $< 5$
- $\geq 5$  to  $< 10$
- $\geq 10$

[REDACTED]

[REDACTED]

[REDACTED]

[REDACTED]

[REDACTED]

[REDACTED]

whose assessment date is closest to the start date of that visit will be used for analyses. If more

[REDACTED]

[REDACTED]

[REDACTED]

[REDACTED]

[REDACTED]

[REDACTED]

[REDACTED]

| [REDACTED]

| [REDACTED]

| [REDACTED]

| [REDACTED]

| [REDACTED]

| [REDACTED]

[REDACTED]

[REDACTED]

[REDACTED]

[REDACTED]

### 2.8.1.1 Handling of missing values

For missing questionnaires no imputation will be undertaken.

[REDACTED]

[REDACTED]

## 2.10 Interim analysis

The protocol described the conduct of an interim analysis of lipids and PCSK9 upon completion of Day 210 for subjects in Group 1 (inclisiran only arm). Although there was a review of data upon completion of Day 210 for subjects in Group 1, no formal interim analysis report was generated. An interim analysis was conducted to evaluate Group 1 safety and tolerability data after all Group 1 subjects completed 24 months of treatment with inclisiran, [REDACTED]

[REDACTED] The interim analysis was not intended for hypothesis testing, hence no sequential testing boundaries were applied.

## 3 Sample size calculation

This is an extension of the Phase II ORION-1 (CKJX839A12201; MDCO-PCS-15-01) study. All eligible and willing subjects who have completed the ORION-1 study to at least Day 210 and whose LDL-C level returned to within 20% of the Baseline of ORION-1 value or who have reached Day 360 can be enrolled into this study. Subjects withdrawn from the ORION-1 study at any time will not be eligible for this study.

## 4 Change to protocol specified analyses

No change from protocol specified analysis was made.

